5.1.2.7 Progression free survival (PFS)

PFS is defined as the time from first treatment with BI 836909 until disease progression or death.

Proprietary confidential information.

© 2018 Boehringer Ingelheim International GmbH or one or more of its affiliated companies. All rights reserved.

This document may not - in full or in part - be passed on, reproduced, published or otherwise used without prior written permission.

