6.2.2 Disease and Response Assessments for Multiple Myeloma

Clinical disease status for multiple myeloma will be assessed at screening, at the start of each cycle as well as at EOT.

At screening and subsequently the evaluation of multiple myeloma will be done according to IMWG (2006).

If a patient has clinical symptoms of multiple myeloma at screening, they should be recorded as baseline conditions.

Biomarkers in blood and urine will be done according to specific [Flow chart](#) for biomarkers.

Total body MRI should be performed within 14 days before day 1, cycle 1; results from routine assessments (MRI) for multiple myeloma are accepted if performed no later than 28 days before start of treatment.

Proprietary confidential information.

© 2018 Boehringer Ingelheim International GmbH or one or more of its affiliated companies. All rights reserved.

This document may not - in full or in part - be passed on, reproduced, published or otherwise used without prior written permission.

Total body MRI should be performed at or within 14 days before day 1, cycle 3; day 1, cycle 5; day 1, cycle 7 as well as every other cycle thereafter and at time of EOT.

Bone marrow aspirates will be done within 14 days before day 1 cycle 1 or at cycle 1, day 1 before start of treatment, when M protein/FLC becomes undetectable during treatment, at day 29 of cycle 3 and at EOT.

For karyotyping the recent analysis will be accepted if performed within 3 months prior to start of study medication in case that no therapy has been given between assessment of karyotyping and study medication; otherwise, a baseline karyotype should be performed at screening; subsequent karyotyping could be performed in subsequent marrow samples.

The biomarker assessments will be performed as specified in the [Flow charts](#). A bone marrow biopsy should be performed if aspirate could not be obtained (punctio sicca).

One sample of bone marrow will be provided for DNA banking in case that the patient has given consent for pharmacogenetic testing (baseline bone marrow, a bone marrow sample on treatment when a complete response is reached).

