6.2.5.3 Extended follow up

In case of ongoing clinical benefit, patients can be followed up to collect data for duration of response. Follow-up visits for responders will be at 3, 6 and 12 months after EOT if a patient did not progress, started a new anti-cancer treatment, died, or withdrew informed consent and will assess related SAEs and AESIs.

Proprietary confidential information.

© 2018 Boehringer Ingelheim International GmbH or one or more of its affiliated companies. All rights reserved.

This document may not - in full or in part - be passed on, reproduced, published or otherwise used without prior written permission.

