6.3 SUBJECT SETS ANALYSED

All entered subjects who received trial medication will be included in the safety analysis and in the pharmacokinetic analysis set depending on the availability of measurement values and on their adherence to the CTP. The criteria for inclusion into these populations are defined as follows:

Populations: Please see below for the specified populations.

Treated set (TS): all patients who were administered study medication. This set of patients is used for all analyses except for analysis of PK data.

[figure not shown]
MTD evaluation set (MTDS): all patients in the TS who were not replaced for the MTD determination. Rules for replacement of patients were defined in CTP, Section 4.1.4.5. In addition safety committee will decide the replacement of patients.

PK Analysis Set (PKS): all evaluable patients in the treated set which provide at least one evaluable observation for at least one PK endpoint.

The TS will be used for all efficacy and safety analyses. In addition, the MTDS represent the populated used for MTD determination. The primary analyses of DLTs during 1st cycle will be based upon the MTDS. PK analyses will be based on the PKS. Refer to Protocol Section 7.3.5 on handling PK endpoints.

Table 6.3: 1 Subject sets analysed

Class of endpoint	Treated set	Subject set	
		MTDS	PKS
Primary and key secondary endpoints	X	primary analysis	
Other secondary and further endpoints	X		
Safety endpoints	X		
Demographic/baseline endpoints	X		
PK endpoints			X

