7.5.2 Other Secondary endpoints

Objective response rate (ORR)

Objective response rate is defined as the percentage of patients achieving a sCR, CR, PR and VGPR as evaluated by the investigator according to the response criteria of the International Myeloma Working Group. The objective response rate will be presented as the proportion of responders, with the exact 95% Clopper-Pearson confidence intervals. The best response (sCR > CR > PR > VGPR) across all assessment will be used and presented.

Duration of response (DOR)

For patients with objective response, the duration of response is calculated from the time of first recorded achievement of a response until documented progression or death. DOR will be summarized descriptively by quartiles if applicable.

Minimal residual disease (MRD) response

MRD response is defined as <1 tumour cell within 10^4 normal cells in bone marrow using FACS analysis. MRD response rate will be calculated as the proportion of patients achieving MRD response with the exact 95% Clopper-Pearson confidence interval.

Duration of MRD response

For patients with MRD response, the duration of MRD response is calculated from the time of first recorded achievement of a MRD response until documented progression or death. Duration of MRD response will be summarized descriptively by quartiles if applicable.

Progression free survival (PFS)

PFS is defined as the time from first treatment with BI 836909 until disease progression or death. For patients who did not have any event (e.g., alive without progression), their PFS will be censored at date of last documented disease assessment. For patients without any events and no disease assessment performed post-baseline, their PFS will be censored at the date of treatment start. PFS will be summarized descriptively by quartiles with 95% confidence interval calculated from Kaplan-Meier estimate.

Pharmacokinetic analyses

The secondary pharmacokinetic endpoints C_{ss} , [REDACTED] will be descriptively explored, [REDACTED]

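### After the residual-effect visit, PFS follow-up depends on response, so the late part of the all-patient Kaplan-Meier curve is likely to rest on responders

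*SAP*

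**What the plan says.** - **Endpoint.** Protocol 5.1.2.7: "PFS is defined as the time from first treatment with BI 836909 until disease progression or death". It is a secondary efficacy endpoint (Protocol 5.1.1; SAP 5.2.2).
- **Analysis set.** SAP 6.3: "The TS will be used for all efficacy and safety analyses", where TS is the treated set.
- **Estimator.** SAP 7.5.2: "PFS will be summarized descriptively by quartiles with 95% confidence interval calculated from Kaplan-Meier estimate". Protocol 7.3.2 leaves the censoring details to the SAP.
- **Censoring.** For patients with no event, "their PFS will be censored at date of last documented disease assessment". The sentence applies to everyone and sets no end to the observation window.
- **Assessments on treatment.** Protocol 6.2.2: "Clinical disease status for multiple myeloma will be assessed at screening, at the start of each cycle as well as at EOT".
- **REP visit.** Protocol 6.2.5.2 collects progression or relapse, death and loss to follow-up from every patient, about 30 days after EOT.
- **After REP.** Protocol 6.2.5.3: "In case of ongoing clinical benefit, patients can be followed up to collect data for duration of response", followed by "Follow-up visits for responders will be at 3, 6 and 12 months after EOT". No progression or survival follow-up is described for a non-responder who stopped without progression.

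The SAP has no rule for this difference in follow-up and no sensitivity analysis. It does not say whether REP status counts as a disease assessment.

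**The concern.** Kaplan-Meier treats a censored patient as having the same later risk as those still under observation. After the REP visit the planned follow-up separates the two groups by response, which is expected to predict progression.

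Take two patients who both stop for toxicity at month 3 and both progress at month 6. The one in partial response can be seen at the 3-month visit and contributes an event. The one with stable disease is last seen at REP, and the progression is never recorded. As patients stop treatment, the risk set comes to consist of responders, while the curve is labelled as PFS in all treated patients.

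The late part of the PFS curve, and above all its third quartile, could therefore look better than it is. Duration of response is not exposed to this, because every patient in that analysis is a responder.

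**Working it through.** The documents state no PFS rate, median, response rate or rate of stopping, so there is no planned figure to reproduce. The size below rests on assumed inputs.

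**From the documents.** Six-week cycles, at most 5, or 10 with ongoing benefit (Protocol 3.1). In months, 5 × 42 / 30.44 = 6.9 and 10 × 42 / 30.44 = 13.8. REP comes about 1 month after EOT. Responder visits run to 12 months after EOT.

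**Assumed.** Exponential PFS within response group, and a constant rate of stopping without progression:
- (a) 30% responders; median PFS 15 months in responders and 3 in non-responders; stopping 0.10 per month; 10-cycle cap for all.
- (b) 40% responders; medians 12 and 4 months; stopping 0.05 per month; 10-cycle cap for all.
- (c) As (b), but non-responders stop at 5 cycles.

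**Formula.** Write π for the group proportion, S for true PFS in the group, λ = ln 2 / median, and G(u) for the probability of still being under observation at time u. In large samples Kaplan-Meier estimates exp(−∫h*(u)du), where h*(u) = Σ π S(u) G(u) λ / Σ π S(u) G(u), summed over the two groups. If G is the same in both groups, this is the true curve.

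**True 12-month PFS.**
- (a) 0.3 × 2^(−12/15) + 0.7 × 2^(−12/3) = 0.172 + 0.044 = 21.6%
- (b), (c) 0.4 × 2^(−12/12) + 0.6 × 2^(−12/4) = 0.200 + 0.075 = 27.5%

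**Results.** Under the planned follow-up, responders are observed to stopping + 12 months. Non-responders are observed to stopping (REP ignored) or to stopping + 1 month (REP counted). Under the common window, everyone is observed to stopping + 1 month.

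| | True | Planned, REP ignored | Planned, REP counted | Common window through REP |
|---|---|---|---|---|
| 12-month PFS (a) | 21.6% | 27.6% | 26.5% | 21.6% |
| 12-month PFS (b) | 27.5% | 30.1% | 29.6% | 27.5% |
| 12-month PFS (c) | 27.5% | 34.7% | 33.1% | 32.0% |
| Third quartile, months (a) | 10.3 | 13.7 | 13.0 | 10.3 |
| Third quartile, months (b) | 13.1 | 14.6 | 14.2 | 13.1 |
| Third quartile, months (c) | 13.1 | 17.7 | 16.9 | not reached |
| Median, months (a) | 4.4 | 4.7 | 4.6 | 4.4 |
| Median, months (b), (c) | 5.9 | 6.2 | 6.1 | 5.9 |

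**Hand check of (c), common window.** Observation is equal up to 6.9 + 1 = 7.9 months. PFS there is 0.4 × 2^(−7.9/12) + 0.6 × 2^(−7.9/4) = 0.253 + 0.153 = 0.406. After that only responders remain, so 12-month PFS is 0.406 × 2^(−4.1/12) = 0.320. At the end of the window, 14.8 months, it is 0.406 × 2^(−6.9/12) = 0.273. This is above 0.25, so the third quartile is not reached.

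**Wider grid.** Simulated with response 20%, 30% or 50%; medians 9 or 12 against 3, 4 or 6 months; stopping 0%, 3% or 8% per month. Planned minus true:

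| Handling of REP | 12-month PFS, all stop by 5 cycles | 12-month PFS, all stop by 10 cycles | Median, 5 cycles (months) |
|---|---|---|---|
| Ignored | +0.04 to +0.09 | 0 to +0.04 | 0 to +1.0 |
| Counted as an assessment | +0.03 to +0.08 | 0 to +0.03 | 0 to +0.6 |
| Events at REP count, but event-free patients censored back at EOT | −0.02 to +0.05 | 0 to +0.03 | −0.5 to +0.2 |

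Under the third handling with 5 cycles, the 9-month difference runs from −0.06 to +0.03. With equal progression risk in responders and non-responders, the first two handlings give no bias and the third a downward one.

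**The case against.** **Follow-up is not lost at EOT.** A reader might infer that only responders are followed once treatment ends. The documents do not support this: the EOT assessment and the REP status check cover everyone. The dependence on response begins after REP.

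**Overstatement is not proven.** A reader might also infer that PFS is certainly too high. That needs non-responders who stop without progression, in some number, and who then progress faster. Patients who stop because of progression, a listed reason in Protocol 3.1, are events and cause no bias. If REP events count while event-free patients are censored back at EOT, an opposite bias appears and can reverse the sign around 9 to 12 months. This stands. It also shows that the SAP leaves the direction open.

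**The censoring sentence is ordinary.** It is worded alike for all patients. The problem comes from combining it with the follow-up rule in Protocol 6.2.5.3.

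**Twelve-month PFS is not a planned output, and sampling error dominates.** The SAP reports quartiles. The first quartile hardly moves and the median moves little; the third quartile does move materially. Protocol 7.2 plans no formal tests, and SAP 6.1 tabulates by dose group, with planned escalation cohorts of 1 or 3 to 6. In one simulated case the standard deviation of estimated 12-month PFS was about 0.08 with 50 patients and 0.22 with 6. All this limits the consequence, but it does not justify an avoidable bias in a reported curve.

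**Responder follow-up is optional.** Protocol 6.2.5.3 says patients can be followed. The calculation assumes every responder has the full 12 months, so lower uptake would shrink the effect.

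**Conclusion.** The point holds in a limited form. Beyond the REP visit, planned observation for progression depends on response, PFS is a Kaplan-Meier estimate in all treated patients, and no section of either document reconciles the two. Late PFS is expected to be overstated if non-responders who stop without progression later progress faster.

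With REP counted as follow-up, the excess in the three scenarios is:
- **12-month PFS:** 26.5 − 21.6 = 4.9 points in (a), 29.6 − 27.5 = 2.1 in (b) and 33.1 − 27.5 = 5.6 in (c).
- **Third quartile:** about 2.6, 1.1 and 3.8 months.
- **Median:** about 0.2 month in each, and at most 0.6 month in the wider grid.

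These sizes depend entirely on the assumed response rate, medians and stopping pattern. The endpoint is secondary and descriptive, and determination of the maximum tolerated dose does not use it.

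**What to change.** In SAP 7.5.2:

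1. Define one PFS observation window for all treated patients, from first treatment through the REP visit.
2. Count progression and death recorded at REP as events. Treat REP status as the last assessment for event-free patients and censor them there. Ending the window at EOT instead would discard progressions and deaths that Protocol 6.2.5.2 collects from everyone.
3. Use the 3, 6 and 12 month responder visits for duration of response and duration of MRD response only, which fits their stated purpose. If PFS using those visits is shown, present it as a supplementary analysis labelled as resting on responders after REP.
4. State the remaining limitation. Treatment beyond cycle 5 requires ongoing clinical benefit (Protocol 3.1), so if non-responders systematically stop there, some bias persists. In (c), 12-month PFS is still 32.0% against a true 27.5%. Equal follow-up of all patients to 12 months after EOT would remove it, but that needs new data collection.

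**Cost.** SAP wording only, with no new data. PFS is not estimated beyond treatment plus REP, and the third quartile may not be reached. Event-free status at the end of the window rests on the REP status check rather than a full response assessment.

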7.7 EXTENT OF EXPOSURE

Extent of exposure will be summarized descriptively by total treatment time (days and number of courses), number of cycles initiated, average number of days of infusion per cycle, number of cycles with at least 14 days of infusion will be calculated; off-drug periods due to non-compliance or toxicity prior to permanent discontinuation will be included as treatment time. Standard descriptive summaries, by treatment group, of these data will be provided for the treated set.

7.8 SAFETY ANALYSIS

All safety analyses will be performed on the treated set (TS). In addition, DLT occurred during course 1 will be tabulated based on the MTD evaluation set (MTDS).

7.8.1 Adverse events

Unless otherwise specified, the analyses of adverse events will be descriptive in nature. All analyses of AEs will be based on the number of subjects with AEs and NOT on the number of AEs.

For analysis multiple AE occurrence data on the CRF will be collapsed into an AE provided that all of the following applies:

- All AE attributes are identical (LLT, intensity, action taken, therapy required, seriousness, reason for seriousness, relationship, outcome, AE of special interest)
- The occurrences were time-overlapping or time-adjacent (time-adjacency of 2 occurrences is given if the second occurrence started on the same day or on the day after the end of the first occurrence).

For further details on summarization of AE data, please refer to [\[3, 4\]](#).

The analysis of adverse events will be based on the concept of treatment emergent adverse events. That means that all adverse events occurring between first drug intake till last drug intake + residual effect period will be assigned to the treatment. All adverse events occurring before first drug intake will be assigned to 'screening' and all adverse events occurring after the residual effect period will be assigned to 'post-treatment' (for listings only). For details on the treatment definition, see [Section 6.1](#).

According to ICH E3 [\[5\]](#), AEs classified as 'other significant' needs to be reported and will include those non-serious adverse events leading to treatment discontinuation or non-serious AEs leading to dose reduction.

An overall summary of adverse events will be presented. This summary will include the first 6 categories from the list below and AEs by highest intensity graded according to CTCAE (version 4.03).

The frequency of subjects with adverse events will be summarised by treatment, primary system organ class and preferred term (mention MedDRA levels to be displayed in the tables).

Separate tables will be provided for patients with each of the following AE categories:

- All AEs,
- DLTs (Course 1 only¹),
- DLTs (All courses),
- AEs leading to dose reduction,

- AEs leading to treatment discontinuation,
- Serious AEs,
- Drug related AEs,
- Drug related serious AEs,
- CTCAE Grade 3 or higher AEs,
- AEs leading to death,

[1]: Course 1 defined by from start of treatment to start of Cycle 2 or the last dose administration of BI 836909 during Cycle 1 + 30 days, whichever occurs earlier.

Separate tables will be provided for subjects with other significant adverse events according to ICH E3 [5], for subjects with adverse events of special interest (only if defined) and for subjects with serious adverse events.

The system organ classes will be sorted alphabetically, preferred terms will be sorted by frequency (within system organ class).

Additional AE tables will be produced for adverse events of special interest (AESIs):

- Infusion-related reactions (CTCAE grade 3 or higher),
- Cytokine release syndromes (CTCAE grade 3 or higher),
- Tumour lysis syndrome,
- CNS adverse events (CTCAE grade 2 or higher),
- DLT,
- Hepatic injury (defined in CTP Section 5.2.2.1).

